### ***12.5.2 Evaluation of Response***

All subjects included in the study will be assessed for response to treatment if they have received at least 3 cycles of therapy.

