### 4.2 Inclusion Criteria

1. Age >18 years.
2. Documented histological or cytological diagnosis of prostate carcinoma.
3. Evidence of metastatic PC on imaging (bone scan and/or CT/MRI scan)
  - a. Patients with liver metastases must have biopsy proven evidence of metastatic prostate cancer in the liver
4. Agree to undergo a biopsy of at least one metastatic site or primary prostate prior to beginning therapy. Adequate archival metastatic tissue can be used if available in lieu of a biopsy if done when patient had CRPC and within 6 months the start of treatment.
5. Agree to undergo a biopsy of at least one metastatic site or primary prostate after 3 weeks of therapy (biopsy must be between day 21 and day 24 of treatment). Re-biopsy of same pre-treatment biopsy soft tissue site especially liver metastases is preferred.
6. Serum testosterone level less than 50 ng/dL. Subjects without prior orchiectomy must be currently taking and willing to continue luteinizing hormone-releasing hormone (LHRH) analogue (agonist or antagonist) therapy until permanent discontinuation of study treatment.
7. Documented progressive metastatic CRPC based on at least one of the following criteria:
  - a. PSA progression according to Prostate Cancer Working Group 3 (PCWG3) criteria
  - b. Objective radiographic progression, according to PCWG3 criteria
8. ECOG performance status of 0-1
9. Recovery to baseline or  $\leq$  Grade 1 CTCAE v4 from toxicities related to any prior treatments, unless specified below or AE(s) are clinically nonsignificant and/or stable on supportive therapy.
10. Adequate organ and marrow function, based upon meeting all of the following laboratory criteria **within 14 days before first dose of study treatment**:
  - a. Absolute neutrophil count (ANC)  $\geq 1500/\text{mm}^3$  ( $\geq 1.5 \text{ GI/L}$ ) without granulocyte colony-stimulating factor support
  - b. White blood cell count  $\geq 2500/\text{mm}^3$  ( $\geq 2.5 \text{ GI/L}$ )
  - c. Platelets  $\geq 100,000/\text{mm}^3$  ( $\geq 100 \text{ GI/L}$ ) without transfusion.
  - d. Hemoglobin  $\geq 9 \text{ g/dL}$  ( $\geq 90 \text{ g/L}$ )
  - e. Total bilirubin  $\leq 1.5 \times \text{ULN}$  (for subjects with Gilbert's disease  $\leq 3 \times \text{ULN}$ )
  - f. Serum albumin  $\geq 2.8 \text{ g/dL}$
  - g. Serum creatinine  $\leq 2.0 \times \text{ULN}$  or calculated creatinine clearance  $\geq 30 \text{ mL/min}$  ( $\geq 0.5 \text{ mL/sec}$ ) using the Cockcroft-Gault equation:

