#### 4.4 Molecular Eligibility

To be eligible, a patient's tumor must have evidence of gene amplification, an activating mutation, or overexpression of one of the following genes: MET, KIT, RET, VEGFR-1, VEGFR-2, VEGFR-3, FLT3, AXL, TRKB, or TIE2. In the event of activating mutations, the observed mutation must be of Level 1, Level 2, or Level 3 as annotated by OncoKB ([www.oncokb.org](http://www.oncokb.org)). Eligibility can be met by **at least one** of the following diagnostic tests:

- 1) DNA sequencing of a metastatic tumor biopsy specimen showing gene amplification or activating mutation using a CLIA-certified assay. Tumor tissue samples must have been collected within 6 months of enrollment.
- 2) Protein overexpression in a metastatic tumor biopsy specimen determined by immunohistochemistry (IHC) showing 3+ protein expression using a CLIA-certified assay. These

- include common in-house KIT and commercial reference labs for panTRK (*e.g.* NeoGenomics) and cMET (*e.g.* NeoGenomics, Caris, Mayo Clinic).
- 3) CLIA-certified commercial cell free DNA assay (either Guardant360 or FoundationOneLiquid assay) reporting gene amplification or activating mutation *within 6 months of enrollment*.
    - a. For the Guardant360 Liquid Biopsy amplification must be at least (++) or (+++) for to meet eligibility.
    - b. For the FoundationOneLiquid assay, amplification will be eligible. Reports that have an “equivocal” or “subclonal” designation will not be eligible.
  - 4) Any non-CLIA certified assay such as RNA expression profiling of a metastatic tumor biopsy specimen showing overexpression must be confirmed by a CLIA-certified assay (*i.e.*, immunohistochemistry showing 3+ protein expression)

Patients who do not meet molecular eligibility criteria will be allowed to enroll if they have liver metastases that meet RECIST criteria for measurable disease. Patients with prostate adenocarcinoma or NEPC will be allowed to enroll.

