## 6 STUDY PROCEDURES

### 6.1 Schedule of Assessments

The study flow chart, including all procedures to be performed during the study, is presented below. Prior to engaging in any study procedure, each patient must sign and date an informed consent form. The following schedule of assessments applies to all subjects; assessments that are more frequent should be obtained if clinically indicated. Cycles are scheduled to be 28 days in length.

If the subject is unable to have a study assessment taken within the defined time window due to an event outside of his or her control (e.g., clinic closure, personal emergency, inclement weather, vacation), the assessment should be performed as close as possible to the required schedule.

Cycle = 28 days	Screening	Cycle 1			Cycle 2	Cycle 3	Cycle 4 +	End of Treatment	Survival Follow-Up
	Day -30 to -1	Day 1	Day 14	Day 21 (+ 3 days)	Day 1 (± 3 days)	Day 1 (± 3 days)	Day 1 (± 3 days)	Post-Treatment	
Informed consent	X								
Medical History 	X								
Physical Exam 	X	X			X	X	X	X	
Vital Signs	X	X	X		X	X	X	X	
Demographics	X								
ECOG Performance Status	X	X			X	X	X	X	
ECG	X								
CBC w. differential and platelet count	X	X			X	X	X	X	
Complete Metabolic Panel 	X	X			X	X	X		
LDH	X	X					X 		
Lipase	X	X 					X 		

 Including cancer history, prior therapy including prior radiotherapy, surgical/pathological reports,

 Including height at baseline and weight at each subsequent visit

 Also include direct bilirubin with known Gilbert's syndrome

	Screening	Cycle 1			Cycle 2	Cycle 3	Cycle 4 +	End of Treatment	Survival Follow-Up
	Day -30 to -1	Day 1	Day 14	Day 21 (+ 3 days)	Day 1 (± 3 days)	Day 1 (± 3 days)	Day 1 (± 3 days)	Post-Treatment	
Cycle = 28 days									
UA and UPCR (24-hr urine, if indicated)	X						X 		
PT/INR and PTT	X								
Thyroid function tests (TSH/FT4 initially. If normal, then TSH thereafter)	X						X 	X	
Testosterone	X						X 	X	
Circulating Immune Activity Sample	X	X 					X 	X	
cfDNA 	X	X 					X 	X	
Tumor assessment (CT/MRI a/p, CT chest bone scan)	X						X 	X 	
PSA sample	X	X					X 	X	
Pre-treatment biopsy 	X								
On-treatment biopsy 				X					
Skeletal-related events 	X	X			X	X	X	X	

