 cfDNA, circulating immune activity, lipase can be collected within 30 days prior to C1D1 or pre-dose C1D1

 When plasma DNA is collected, it should be collected as close to biopsy date as possible, including same day. In the event it is collected on the same day, the specimen should be acquired *prior* to the biopsy procedure.

 Every 12 weeks (± 5 days) until disease progression. For EOT, does not have to be repeated if done within 6 weeks of visit.

 Assess continuously until disease progression

 Every 12 weeks beginning with C4D1 (e.g. C4, C7, C10, etc).

 Collect only on C4D1

 Pre-treatment biopsy can be waived provided that adequate archival material for molecular analyses available from biopsy performed within 3 months of enrollment

 On-treatment biopsy during cycle 1 after 3 weeks of therapy. Biopsy must be performed between day 21 and day 24 on therapy (inclusive). *NB: cabozantinib must be held 5 days before and 5 days after biopsy*

Cycle = 28 days	Screening	Cycle 1			Cycle 2	Cycle 3	Cycle 4 +	End of Treatment	Survival Follow-Up
	Day -30 to -1	Day 1	Day 14	Day 21 (+ 3 days)	Day 1 (± 3 days)	Day 1 (± 3 days)	Day 1 (± 3 days)	Post-Treatment	
Concomitant medications 	X	X			X	X	X	X	
Adverse events 	X	X	X		X	X	X	X	
Health Care Resources 	X	X			X	X	X	X	
Cabozantinib dosing 		X			X	X	X		
Dispense/return of oral study drug and compliance accounting		X			X	X	X	X	
Additional cancer treatment, survival status								X	Subjects will be followed every 12 weeks for 2 years after completion of the study or until death, whichever occurs first

 Document those taken from 30 days prior to treatment through 30 days after the decision to discontinue study treatment

 Document new or worsening events from time of informed consent through 30 days after the last dose of study treatment (related SAEs at any time). Adverse events information will be collected at study visits and may also be collected at any time over the phone or by spontaneous subject report. At study visits where any study treatment is administered, adverse events will be documented pre- and post-dose. Certain AEs and all SAEs that are ongoing 30 days after last dose of study treatment are to be followed until resolution or determination by the investigator that the event is table or irreversible.

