### **7.10 Duration of Therapy and Criteria for Removal from Study**

Subjects may discontinue study treatment or withdraw their consent to participate in the study at any time without prejudice. The investigator may withdraw a subject from study treatment or from the study if, in his or her clinical judgment, it is in the best interest of the subject or if the subject cannot comply with the protocol.

In addition, any of the following conditions require discontinuation of the subject from study treatment:

- An AE or intercurrent illness that in the opinion of the investigator warrants the subject's withdrawal from study treatment;
- The investigator believes it is not in the best interest of the subject to continue on study
- Specific conditions described in the Management of Adverse Events Section;
- Necessity for treatment with other anticancer treatment prohibited by protocol;
- Sexually active subjects who refuse to use medically accepted barrier methods of contraception (e.g., male condom, female condom) during the course of the study and for 4 months after discontinuation of study treatment;

- If the subject does not recover from his or her toxicities to tolerable Grade  $\leq 2$  within 6 weeks, the subject will have study treatment discontinued unless there is unequivocal evidence that the subject is benefitting. In this situation, a subject may be able to restart therapy with a dose reduction upon resolution of the toxicity and with agreement of the principal investigator / Sponsor;
- Request by regulatory agencies for termination of treatment of an individual subject or all subjects under the protocol;
- Significant noncompliance with the protocol schedule in the opinion of the investigator;
- Subjects who cannot tolerate the minimum protocol-specified dose of study treatment will have study treatment discontinued;
- Progressive disease (PD) or the subject no longer experiences clinical benefit as determined by the investigator

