### ***12.3.2 Analysis of Secondary Endpoints***

The median OS will be estimated using Kaplan-Meier methodology. Greenwood's formula will be used to calculate 95% CIs for the Kaplan-Meier estimates. The proportion of men with a meaningful decrease in PSA from baseline (30% and 50% declines will both be used) will be summarized with a binomial point estimate and corresponding 95% binomial CI. Likewise, the proportion of patients with a tumor response (modified RECIST response of CR or PR) will also be estimated with a binomial point estimate and 95% CI.

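### Limiting response assessment to patients with at least 3 cycles drops early failures from the denominator and biases the response proportion upward relative to an all-treated rate

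*Combined protocol and SAP*

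**What the plan says.** - **Who is assessed.** Section 12.5.2, under the heading on reporting and exclusions: "All subjects included in the study will be assessed for response to treatment if they have received at least 3 cycles of therapy".
- **What is estimated.** Section 12.3.2 summarises "the proportion of patients with a tumor response (modified RECIST response of CR or PR" as a binomial estimate with a 95% CI. It names no analysis set, and no other section defines an all-treated set for response or says that unassessed patients are non-responders.
- **Timing.** Section 6.1: "Cycles are scheduled to be 28 days in length". Tumor assessments first appear on treatment in the Cycle 4+ column, with the footnote "Every 12 weeks (± 5 days) until disease progression".
- **Scans after early stopping.** The same footnote adds, for the end-of-treatment visit, "For EOT, does not have to be repeated if done within 6 weeks of visit". Section 10.1 also allows unscheduled assessments.
- **Reasons to stop.** Section 7.10 includes "Progressive disease (PD) or the subject no longer experiences clinical benefit as determined by the investigator", alongside adverse events.
- **A second exclusion.** Section 12.2 replaces certain patients who withdraw before a full 28 days and leaves them out of the analysis. Read literally, it covers those who did have the on-treatment biopsy.
- **Role of response.** It is the primary objective in 1.2.1. Section 12.1 makes rPFS the primary endpoint and lists tumor response as secondary.
- **Measurable disease.** Section 4.2 accepts "Evidence of metastatic PC on imaging (bone scan and/or CT/MRI scan". Section 4.4 admits patients without a qualifying alteration "if they have liver metastases that meet RECIST criteria for measurable disease", and asks for measurable disease of no one else.

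**The concern.** The rule selects patients on something that happens after treatment starts: staying alive and on drug for 84 days. Those who do worst in that period had little chance to show a response, and they are removed from the denominator rather than counted as failures. A patient with progression documented on an end-of-treatment scan at week 8 would not count at all.

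The trial has a single arm, so there is no control group in which the same exclusion could offset the bias. A reader would naturally set the reported rate beside rates computed in all treated patients, and the comparison would favour this trial. If the same set feeds the responder versus non-responder comparisons in 12.4, the patients with early resistance also drop out of the biomarker work.

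**Working it through.** **The plan's own figure.** No precision is stated for response. The only interval in section 12 concerns rPFS: 31.1-68.9% for a 50% probability with 28 patients. It reproduces as 0.5 ± 2 × √(0.25/28) = 0.5 ± 0.189. It says nothing about the response denominator.

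**Step 1: the threshold and the first scan coincide.** 3 cycles × 28 days = 84 days = 12 weeks, which is also the first scheduled on-treatment scan (± 5 days). A patient who stops before 84 days has, on the fixed schedule, no post-baseline scan and is not assessed under 12.5.2.

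**Step 2: effect on the proportion.** Let N be the patients treated, x the responders and e the patients excluded, with no responders among the e. The rate moves from x/N to x/(N − e), a factor of N/(N − e) that does not depend on x. N = 30 is from 12.2. The values e = 3, 6, 9 and x = 6 are assumptions. Intervals are exact (Clopper-Pearson).

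| Excluded (assumed) | Factor | Proportion | 95% CI |
|---|---|---|---|
| 0 (all treated) | 1.00 | 6/30 = 20.0% | 7.7-38.6% |
| 3 | 30/27 = 1.11 | 6/27 = 22.2% | 8.6-42.3% |
| 6 | 30/24 = 1.25 | 6/24 = 25.0% | 9.8-46.7% |
| 9 | 30/21 = 1.43 | 6/21 = 28.6% | 11.3-52.2% |

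With N = 28 (the planned maximum with liver metastases, 12.1) the factors are 28/25 = 1.12, 28/22 = 1.27 and 28/19 = 1.47.

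**Step 3: when the direction holds.** If r of the excluded patients had responded on an early scan, the 3-cycle rate is (x − r)/(N − e). This exceeds x/N whenever r/e < x/N, that is, whenever excluded patients respond less often than the whole group. With e = 6 and r = 1 the rate is 5/24 = 20.8%, still above 20.0% but only just. Since those excluded mostly stopped for failure or toxicity before any scheduled scan, r is expected to be near zero.

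**Step 4: how many might be excluded.** The documents do not say. As a rough upper guide, assume exponential rPFS with the two medians that come from cabozantinib-containing treatment. 84 days = 84/30.4375 = 2.76 months.

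- Median 5.6 months (section 12, historical control): 1 − 0.5^(2.76/5.6) = 28.9%, or 8.7 of 30.
- Median 6.2 months (section 2.2.1, liver metastases, combination with atezolizumab): 1 − 0.5^(2.76/6.2) = 26.5%, or 8.0 of 30.

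These are shares with an rPFS event by day 84, not shares with fewer than 3 cycles. Much radiographic progression would first be seen on the 12-week scan, in patients who have completed 3 cycles and stay in the denominator.

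**Step 5: the opposite pull.** Section 10.2 defines CR and PR on target soft-tissue lesions, and 10.4 scores bone only by whether new lesions appear. A molecularly eligible patient with bone-only disease can complete 3 cycles and enter the denominator without being able to score CR or PR by target lesions. That lowers the proportion. The number of such patients is not given, so no net effect can be calculated.

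**The case against.** The strongest reply is that the statistical section makes rPFS the primary endpoint, estimated by Kaplan-Meier, and that 12.5.2 speaks only of response. Tumor response there is a descriptive secondary estimate with no threshold attached. This stands as a limit on scope: a reader might infer that the rule also distorts rPFS, and the text does not clearly say so. It does not remove the point, because 1.2.1 makes the response proportion the primary objective and 12.3.2 gives no other denominator.

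Second, patients who stop early are not without imaging, since end-of-treatment and unscheduled scans are provided for. That is correct, but under 12.5.2 those scans do not bring the patient back into the assessment, so the rule discards observed data.

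Third, the size can easily be overstated. Section 2.2.1 also gives a median PFS of 2.1 months in patients with liver metastases, and a reader might infer from it that about 60% fail before week 12. That median belongs to the control arm on a second novel hormonal therapy, not to cabozantinib. Even the 26.5-28.9% guide is not the share excluded.

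Fourth, a reader might conclude that the result could not be compared with any other trial. The documents describe no other trial's response denominator, so this is unsupported. What follows is narrower: comparison with an all-treated rate would be biased.

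Finally, bone-only patients pull the other way. With up to 28 of 30 patients planned to have liver metastases, their number may be small, and 10.2 can be read as tying CR/PR to measurable disease, although 12.3.2 does not say so.

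**Conclusion.** The rule is wrong as written. Section 12.5.2 is the only statement of who enters the response proportion, and it removes patients who fail or stop before 84 days instead of counting them as non-responders. The resulting proportion is biased upward relative to an all-treated rate, provided excluded patients respond less often than the rest, which the timing of the scans makes very likely.

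The size is not in the documents. The factors of 1.11 to 1.43 rest on an assumed 3 to 9 exclusions out of 30 with no responders among them; the percentages also assume 6 responders. The 26.5-28.9% is a rough upper guide that assumes exponential rPFS.

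The bias described is that of the 3-cycle rule alone. The missing requirement for measurable disease is a separate and smaller matter with the opposite sign, and the net effect of the two is unknown.

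**What to change.** 1. Replace 12.5.2, and refer to it from 12.3.2, with wording such as: *The response proportion will be calculated in all subjects who received at least one dose of cabozantinib. Subjects without an evaluable post-baseline tumor assessment will be counted as non-responders. End-of-treatment and unscheduled scans will be used.*
2. Align 12.2, so that a patient who withdraws before 28 days stays in this analysis even if he is replaced. Otherwise the two sections would contradict each other.
3. Keep the set with at least 3 cycles, if wanted, as a supportive analysis labelled as such.
4. Separately, say how patients without measurable soft-tissue disease are handled. Either report CR/PR among treated patients with measurable disease at baseline, acknowledging that this narrows the population in 1.2.1, or report both denominators. Make the choice before the response data are examined.

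The cost is a change of wording and a less favourable response figure. No extra patients, scans or visits are needed.

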## **13. ADVERSE EVENT REPORTING REQUIREMENTS**

Adverse event (AE) monitoring and reporting is a routine part of every clinical trial. The investigator will be required to provide appropriate information concerning any findings that suggest significant hazards, contraindications, side effects, or precautions pertinent to the safe use of the drug or device under investigation. Safety will be monitored by evaluation of adverse events reported by subjects or observed by investigators or research staff, as well as by other investigations such as clinical laboratory tests, x-rays, electrocardiographs, etc.

### **13.1 Adverse Event Definition**

An adverse event (also referred to as an adverse experience) can be any unfavorable and unintended sign (e.g., an abnormal laboratory finding), symptom, or disease temporally associated with the use of a drug and does not imply any judgment about causality. An adverse event can arise with any use of the drug (e.g., off-label use, use in combination with another drug) and with any route of administration, formulation, or dose, including an overdose.

#### ***13.1.2 Adverse Events (AEs)***

An AE is any untoward medical occurrence in a patient or clinical trial subject administered a medicinal product and which does not necessarily have a causal relationship with this treatment. An adverse event can therefore be any unfavorable and unintended sign (e.g. an abnormal laboratory finding), symptom, or disease temporarily associated with the use of a medicinal product, whether or not considered related to the medicinal product. An adverse event can arise from any use of the drug (e.g. off-label use, use in combination with another drug) and with any route of administration, formulation, or dose, including an overdose. This definition also includes AEs associated with medication errors and uses of the investigational product outside what is in the protocol, including misuse and abuse. Pre-existing medical conditions that worsen during the study should be recorded as AEs. Abnormal laboratory values, ECG findings, or vital signs are to be recorded as AEs if they meet the criteria described in this protocol. All untoward events that occur after informed consent through 30 days after the decision to discontinue study treatment (or the date the subject is deemed to be a screen failure) are to be recorded by the investigational site. This requirement includes AEs from unscheduled as well as scheduled visits and includes the new onset of or increase in pain during this period.

Adverse event terms recorded on the CRFs will be mapped to preferred terms using the Medical

Dictionary for Regulatory Activities (MedDRA). Seriousness, severity grade, and relationship to study treatment will be assessed by the investigator. Severity grade will be defined by the current version of the National Cancer Institute (NCI)-Common Terminology Criteria for Adverse Events (CTCAE).

